3.0 Background*

Substance use science-to-service gap needs to close for the underserved aging with HIV. Many effective interventions do not translate into meaningful outcomes that improve patient care. Therefore, NIDA and the Office of AIDS Research have prioritized research that promotes the uptake of evidence-based interventions into real-world settings. In order to provide effective patient-centered care, effective interventions need to reach those in need. In particular, substance use interventions have lagged in moving from the bench (research labs) to the community (real-world settings). Extant literature suggests that peer navigators may improve treatment engagement among substance users and thereby has the potential to improve the effectiveness of SBIRT in this population in particular.

Florida provides the opportunity to implement substance use interventions among older HIV-positive adults. In Florida 42% of people living with HIV are aged 50 years and older compared to 31% in the rest of the United States. While cART has transformed HIV into a manageable chronic condition, leading to a large population aging with the disease, people aging with HIV continue to engage in high risk behaviors. At this stage in the HIV epidemic, we must use available evidence-based tools to meet the needs of those aging with HIV. Older adults living with HIV misuse alcohol and illicit drugs at rates higher than the general population. In addition, HIV+ adults aged 50 years and older are likely to be frailer than their chronological age indicates due to their

PROTOCOL TITLE: Feasibility of Brief Intervention for HIV+ Adults 50+ in Primary Care Settings

disease status, which makes them more vulnerable to the consequences of substance misuse (i.e., greater intoxication even with lower levels of consumption). Further, substance misuse is associated with decreased medication adherence, decreased engagement in HIV care, more medical co-morbidities, higher rates of depression, and poorer quality of life. Extant research suggests depression and pain are considered motivators of misuse and may make patients less responsive to interventions.

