6.0 Procedures Involved*

Recruitment/Sampling: Patients will be recruited using convenience sampling technique from HIV primary care clinics with whom the PI works regularly: the Columbia County Department of Health (Lake City, FL) and the CAN Community Health Clinic (Jacksonville, FL)

Preliminary Screen: Patients will be prescreened for eligibility using a computerized screening tool, NIDA Modified Alcohol, Smoking, Substance Involvement Screening Test [NM-ASSIST], to assess substance misuse risk level. All clinic patients will have the opportunity to complete the substance use screening assessment after checking in for their appointment. All who score moderate and above on the alcohol or illicit substance portion of the NM-ASSIST and meet eligibility criteria will be referred to the study. We will train all recruiters (clinic staff) to provide an extensive explanation of why we are offering these services, as the patients may not perceive themselves as having a substance misuse issue.

Baseline Assessment Procedures: Following a successful initial screen, study staff will explain the procedures of the study and obtain informed consent. All study activities will be conducted in a private room in the clinic. The research assistant (RA) performing the assessment will verify the patient's complete understanding of the informed consent form and all study procedures. Following informed consent, patients will complete the baseline assessment. The baseline assessment will consist of urine drug screen and a series of research questionnaires delivered on a mobile device. The research questionnaires include information on: substance use, substance use treatment, HIV treatment engagement, depression, and pain. The assessment is relatively brief in order to maximize willingness to participate and decrease patient burden. The assessment will take approximately 30 minutes to complete. The questionnaires will be given in a computerized. The iPad/tablet will use REDCap survey software, which provides direct, encrypted transfer of information via internet to a secure study server.

Three and Six Month Follow-Up Assessment: *Participants will be contacted three and six months post-intervention to schedule an in-person follow-up assessment. We will evaluate substance use treatment engagement post intervention and substance use (self-report and urine toxicology analysis). Participants will be compensated \$30 for each*

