17.0 Data Management* and Confidentiality

Analysis Plan

Aim 1: Feasibility will be calculated as described above. The model will be considered feasible if 80% of the target population has been reached.

Aim 2: Acceptability scores will be calculated for all participants as listed above to determine overall acceptability of the SBIRT model. Sub analyses will be conducted for disease type and HIV x age using calculations listed above. Acceptability will be examined by disease type HIV vs. non-HIV. Acceptability will also be examined for HIV only by younger (<49) versus older (>50).

Aim 3: This pilot is a randomized two groups (SBIRT-PN vs. TAU) with repeated measures (baseline and 3 and 6-month follow-ups) design. We will clean the data, examine variable distributions, compute descriptive statistics, examine outliers, and examine the effectiveness of randomization prior to analyses of specific aims to ensure the underlying assumptions of normality and equal variance have not been violated. Before testing each secondary outcome, we will examine whether intervention and control group participants differ on potential confounding variables at study entry. We will control for a variable if it differs by condition on the outcome variable being tested in that analysis at $p < .05$. Using chi-square (or t-test for continuous variables) we will examine the associations between the dependent variables and relevant demographic variables. All analyses will employ an intent-to-treat approach.

Our first step will be to see if the intervention influenced formal engagement in substance use treatment. Using chi-square analyses we will examine group difference on engagement in formal treatment (0=no treatment/1=treatment confirmed). To test the remainder of the hypothesis, analyses will rely on mixed model repeated measures ANOVA since the relatively small sample size is likely to prohibit more sophisticated statistical modeling. Hypotheses testing rely on inspection of F values and associated p values. A mixed model ANOVA is used to test for differences between two or more independent groups while subjecting participants to repeated measures. In the current analyses the fixed effect will be group condition (SBIRT-PN or TAU) and the random effect will be number of drug use days in the past 3 and 6 months.

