Missing Data. We will handle missing data values with a 3-step process. First, the dropout rates will be compared across the groups with chi-square analyses to assess systematic differences due to condition. Second, demographic and dependent variables will be examined for their relationship to dropout. Those variables related to dropout status will be used to impute missing values for use in the analyses described (via SPSS Missing Items Analysis). Finally, comparison of the completers vs. imputation analyses will yield an additional estimate of the effect of dropouts on hypothesis tests.

Confidentiality Safeguards

PROTOCOL TITLE: Feasibility of Brief Intervention for HIV+ Adults 50+ in Primary Care Settings

To ensure confidentiality, all information will be coded so that it cannot be associated with any individual. A master sheet, with individual names and their respective code numbers will be kept in a locked file that can be accessed only under supervision of the PI. All data entered into the computerized database will be identifiable by subject code number only. No one outside of the lead research team will have access to records identifying participants' names at any time. The information gathered will be used only for scientific, educational, or instructional purposes.

Data Safeguards

Any computer files with identifying data, such as subject logs needed to match data to names over time, will be protected by multiple passwords. During the analysis of the data, all identifying information with the exception of the subject identification number is removed from the data.

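### Baseline depression and pain are collected and described as prognostic, but the imputation rule leaves them out and Aim 3 does not prespecify them as covariates

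*Protocol*

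**What the plan says.** Protocol section 6.0 (Baseline Assessment Procedures) lists what is measured at entry: "The research questionnaires include information on: substance use, substance use treatment, HIV treatment engagement, depression, and pain". Section 3.0 gives the reason for interest in two of these: "depression and pain are considered motivators of misuse and may make patients less responsive to interventions".

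The missing-data text in Protocol section 17.0 has three steps. Dropout is compared between arms. Then "demographic and dependent variables will be examined for their relationship to dropout", and the variables found to be related to dropout supply the imputation. Last, completer results are compared with imputed results. The SAP has no missing-data text.

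For Aim 3, Protocol section 17.0 and the SAP describe the drug-use model in the same terms, with arm as the only fixed effect named: "In the current analyses the fixed effect will be group condition (SBIRT-PN or TAU"). Both documents also screen an unnamed set of possible baseline confounders and adjust for those that meet a p < .05 rule. Protocol section 6.0 (Randomization) adds that baseline differences will be checked and adjusted for if needed. No analysis text in either document names depression or pain.

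**The concern.** The protocol gives its own reason to think that depression and pain are related to substance use and to response, and it pays the cost of measuring them. The written imputation rule cannot use them, even if they turn out to predict strongly who leaves.

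That matters if depressed patients are retained differently by arm. The intervention session in Protocol section 5.0 assigns a peer navigator and can direct patients to mental health counselling, and section 3.0 suggests that navigators may improve engagement. Differential retention is therefore conceivable. Were it to happen, imputation without depression would give a distorted arm difference.

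Separately, a covariate that predicts the outcome narrows the Aim 3 interval whether or not it happens to be imbalanced. A rule based on imbalance gives up that gain most of the time.

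**Working it through.** The documents give no effect size, SD or power calculation for Aim 3, so there is no stated figure to reproduce.

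**1. Are the two scores in the imputation pool?** The pool holds demographic and dependent variables. Depression and pain are not demographic. The secondary outcomes (Protocol section 4.0) and the follow-up assessments (section 6.0) cover treatment engagement and substance use, so the two scores are not dependent variables either. No other text reopens the pool. The Aim 3 confounder screen concerns the outcome model, not the imputation.

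**2. How often would Aim 3 adjust for them?** Read as a test of baseline difference between arms, the p < .05 rule admits a given variable about 5% of the time under randomisation. For two independent variables, the chance that at least one enters is 1 − 0.95² = 0.0975. About 90% of the time neither is adjusted for. Prognostic strength plays no part.

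**3. Possible dropout bias.** From the protocol: 90 patients, so about 45 per arm, with dropout of 10% expected and 20% at most (section 25.0, Retention). Assumed: 20% dropout in TAU, with log odds rising linearly in a standardised depression score D (odds ratio 1.5 to 2.5 per SD); 10% dropout in SBIRT-PN unrelated to D; outcome slope 0.2 to 0.4 SD per SD of D; true effect 0.4 SD.

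Approximate bias = slope × mean of D among TAU completers. Integrating the logistic dropout model over a standard normal D gives a mean of −0.079 at odds ratio 1.5 and −0.162 at odds ratio 2.5. The corners are 0.2 × 0.079 = 0.016 SD and 0.4 × 0.162 = 0.065 SD, both towards no effect.

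A simulation (45 per arm, 4,000 runs per setting, regression imputation with arm and baseline outcome) gave these biases, in SD, without and with depression in the imputation:

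| Slope | OR 1.5: without / with | OR 2.5: without / with |
|---|---|---|
| 0.2 | 0.014 / −0.009 | 0.037 / −0.002 |
| 0.3 | 0.020 / −0.001 | 0.052 / 0.003 |
| 0.4 | 0.024 / 0.001 | 0.070 / 0.000 |

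As a share of the assumed effect, this is 0.014/0.4 = 3.5% to 0.070/0.4 = 17.5%. Letting baseline substance use (slope 0.5 on the outcome) correlate 0.2 with depression gives 0.013 to 0.063 SD without depression. A correlation of 0.3 gives 0.012 to 0.057 SD. Having the baseline outcome in the imputation therefore removes only part of the bias.

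**4. When the bias disappears.** With 20% dropout and odds ratio 2 in both arms, the mean of D among completers is −0.129 in each, so the difference is 0. With odds ratio 2 in both arms but 20% versus 10% dropout, the means are −0.129 and −0.066; at slope 0.2 the bias is 0.2 × 0.063 = 0.013 SD. With equal dropout and a 0.2 SD treatment interaction it is 0.2 × 0.129 = 0.026 SD.

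**5. Against the noise.** At 20% dropout, 90 × 0.8 = 72 patients remain, or 36 per arm, and the unadjusted standard error is √(2/36) = 0.236 SD. With baseline adjustment in simulation it is about 0.19 SD. The largest bias is 0.070/0.19 = 0.37 of a standard error.

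**6. Precision.** If the two scores explain a share R² of residual variance, adjustment is worth 90/(1 − R²) patients and multiplies the standard error by √(1 − R²). At an assumed R² of 0.03: 90/0.97 = 92.8 patients, factor 0.985. At 0.10: 90/0.90 = 100 patients, factor 0.949. The standard error is about 1.5% to 5% smaller.

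**The case against.** A reader might infer that depression and pain are shut out of Aim 3 and that no analysis can use them. The documents do not support that. The confounder list in Protocol section 17.0 and the SAP is open, and section 6.0 allows adjustment for baseline differences, so either score could enter. What stands is that entry is not prespecified and depends on a test of imbalance. The rule is also hard to read, because it refers to differences on the outcome variable.

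A reader might also infer that the trial will carry dropout bias. That is not shown either. Section 3.0 says only that the two factors may reduce response; it does not say that they cause the outcome or predict dropout. The bias in the table needs depression to drive dropout in one arm only, and nothing in the documents points to that pattern. Even then the gain is modest: in a simulation of the same scenario with a baseline correlation of 0.3, including depression lowered root mean squared error from 0.190 to 0.189 at the low end and from 0.193 to 0.182 at the worst corner.

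The missing-data steps offer some protection. Comparing dropout by arm could flag a 20% versus 10% split, and baseline substance use carries part of any depression signal. The completer-versus-imputed comparison helps less. If neither analysis conditions on depression, both carry similar bias, and agreement between them would reassure falsely.

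Finally, Aim 3 is a secondary aim of a feasibility pilot, and no decision threshold hangs on it. That limits the weight of the point but does not answer it.

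**Conclusion.** The point holds as a minor, inexpensive improvement. As written, the imputation rule omits two baseline variables that the protocol itself regards as relevant, and Aim 3 leaves adjustment for them to a screen that would include neither about 90% of the time.

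Dropout bias is a risk, not a finding. It is about 0.01 to 0.07 SD under the assumed one-arm pattern, against a standard error of about 0.19 to 0.24 SD. It is about zero when the dependence and the dropout rates match across arms and there is no treatment interaction. The precision gain, equivalent to 93 to 100 patients instead of 90, rests on an assumed 3% to 10% of residual variance explained. The dropout odds ratios, outcome slopes and variance shares are all assumptions; the documents give none of them.

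**What to change.** Make two wording changes.

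- In Protocol section 17.0, Missing Data, second step: state that the imputation model always includes arm, baseline substance use, baseline depression and baseline pain, whether or not they pass the dropout screen. Other variables can still be added through the screen.
- In Aim 3 of Protocol section 17.0 and of the SAP: name baseline depression and pain as covariates in the drug-use model, in place of leaving their entry to the p < .05 screen.

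No new data are needed. The cost is two degrees of freedom in a 90-patient model. If the sponsor wants to keep covariates to a minimum, the missing-data change can stand alone and is the better supported of the two.

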7.0 Data and Specimen Banking*

[figure not shown]
N/A.

8.0 Sharing of Results with Subjects*

N/A.

9.0 Study Timelines*

Figure 2: Schematic Overview of Study Procedures

10.0 Subject Population*

Participants will be 90 patients recruited through DOH Columbia County and CAN Community Health.

Study inclusion criteria includes that patients must be:

1. HIV-positive (seropositive confirmed by medical records).
2. Arrive for a clinic visit with an HIV physician.
3. Have a substance misuse screening score indicating moderate or high risk.

Persons will be ineligible if they:

1. are unable to interview and consent in English
2. unwilling or unable to participate in follow up
3. currently in addiction treatment
4. have a medical marijuana prescription

11.0 Vulnerable Populations*

N/A.

12.0 Local Number of Subjects

N= 90

13.0 Recruitment Methods

We will recruit participants from patients attending the primary care clinic for routine medical appointments. Patients will be prescreened for eligibility using a computerized screening tool, NIDA Modified Alcohol, Smoking, Substance Involvement Screening Test [NM-ASSIST], to assess substance misuse risk level. All clinic patients will have the opportunity to complete the substance use screening assessment after checking in for their appointment. All who score moderate and above on the alcohol or illicit substance portion of the NM-ASSIST and meet eligibility criteria will be referred to the study. We will train all recruiters (clinic staff) to provide an extensive explanation of why we are offering these services, as the patients may not perceive themselves as having a substance misuse issue)

Participants will be compensated \$30 for each assessment which includes the baseline visit and two follow up visits for a total of \$90 of compensation throughout the entire six month study period

14.0 Withdrawal of Subjects*

Participants may be withdrawn from the study without consent for the following reasons:

- Participants who tell us that they are going to hurt him or herself or someone else will be withdrawn from the study. These participants will be referred to community based agencies that provide counseling and treatment services.
- The Principal Investigator can withdraw participants from this study for unanticipated reasons.

15.0 Risks to Subjects*

Possible Discomforts and Risks: Questions may be unpleasant or difficult for participants to answer. Additionally, despite taking appropriate steps to safeguard collected information, there is a slight risk that participant information could be revealed accidentally or inappropriately. This release of information may upset a participant or even affect their insurability or employability. A Certificate of Confidentiality will be obtained from the National Institute of Drug Abuse to assist us in protecting participant information.

16.0 Potential Benefits to Subjects*

Participants may benefit from information about substance misuse and how it could negatively affect their mental and physical health.

Participants may also benefit from tips and strategies that decrease substance misuse

17.0 Data Management* and Confidentiality

Analysis Plan

Aim 1: Feasibility will be calculated as described above. The model will be considered feasible if 80% of the target population has been reached.

Aim 2: Acceptability scores will be calculated for all participants as listed above to determine overall acceptability of the SBIRT model. Sub analyses will be conducted for disease type and HIV x age using calculations listed above. Acceptability will be examined by disease type HIV vs. non-HIV. Acceptability will also be examined for HIV only by younger (<49) versus older (>50).

Aim 3: This pilot is a randomized two groups (SBIRT-PN vs. TAU) with repeated measures (baseline and 3 and 6-month follow-ups) design. We will clean the data, examine variable distributions, compute descriptive statistics, examine outliers, and examine the effectiveness of randomization prior to analyses of specific aims to ensure the underlying assumptions of normality and equal variance have not been violated. Before testing each secondary outcome, we will examine whether intervention and control group participants differ on potential confounding variables at study entry. We will control for a variable if it differs by condition on the outcome variable being tested in that analysis at $p < .05$. Using chi-square (or t-test for continuous variables) we will examine the associations between the dependent variables and relevant demographic variables. All analyses will employ an intent-to-treat approach.

Our first step will be to see if the intervention influenced formal engagement in substance use treatment. Using chi-square analyses we will examine group difference on engagement in formal treatment (0=no treatment/1=treatment confirmed). To test the remainder of the hypothesis, analyses will rely on mixed model repeated measures ANOVA since the relatively small sample size is likely to prohibit more sophisticated statistical modeling. Hypotheses testing rely on inspection of F values and associated p values. A mixed model ANOVA is used to test for differences between two or more independent groups while subjecting participants to repeated measures. In the current analyses the fixed effect will be group condition (SBIRT-PN or TAU) and the random effect will be number of drug use days in the past 3 and 6 months.

Missing Data. We will handle missing data values with a 3-step process. First, the dropout rates will be compared across the groups with chi-square analyses to assess systematic differences due to condition. Second, demographic and dependent variables will be examined for their relationship to dropout. Those variables related to dropout status will be used to impute missing values for use in the analyses described (via SPSS Missing Items Analysis). Finally, comparison of the completers vs. imputation analyses will yield an additional estimate of the effect of dropouts on hypothesis tests.

Confidentiality Safeguards

PROTOCOL TITLE: Feasibility of Brief Intervention for HIV+ Adults 50+ in Primary Care Settings

To ensure confidentiality, all information will be coded so that it cannot be associated with any individual. A master sheet, with individual names and their respective code numbers will be kept in a locked file that can be accessed only under supervision of the PI. All data entered into the computerized database will be identifiable by subject code number only. No one outside of the lead research team will have access to records identifying participants' names at any time. The information gathered will be used only for scientific, educational, or instructional purposes.

Data Safeguards

Any computer files with identifying data, such as subject logs needed to match data to names over time, will be protected by multiple passwords. During the analysis of the data, all identifying information with the exception of the subject identification number is removed from the data.

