Randomization: We will use Block random assignment (blocks of 4 by each recruitment site) to ensure equal numbers are assigned to each condition by site. Randomization should create groups with equal characteristics with respect to disease related and medical variables. However, we will assess for baseline differences prior to conducting any analyses and control as necessary.

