Attrition is a significant concern in an implementation trial. First, we will develop a strong collaborative relationship between participants and members of the research team. This is a critical component of our retention strategy, beginning at the moment of first contact between the recruiter and potential participant. Second, we will ensure that participants understand that they are making a contribution and that their efforts have the potential to improve other people's experiences. Participants will receive study newsletters and flyers containing useful and pertinent information on wellness management and other related resources and local events. Finally, we will obtain secondary contact information and will use multiple communication channels (email, phone, text messaging, social media) to maintain contact with study participants. We have budgeted research staff time for tracking and follow-up of participants. One RA will dedicate 20% time to patient tracking during recruitment and follow up phase. Based on our prior work using these strategies with this patient population, we anticipate a 10% dropout rate with a maximum dropout rate of 20% by time 3.

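### The imputation rule does not guarantee randomised arm a place in the model, so imputed Aim 3 effects would normally be shrunk by about 10% to 20%

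*Protocol*

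**What the plan says.** The only missing-data rule is in Protocol section 17.0, under Missing Data. It has three steps.

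- Step 1: "First, the dropout rates will be compared across the groups with chi-square analyses to assess systematic differences due to condition". No significance level is given, and no consequence for the imputation is stated.
- Step 2: "Second, demographic and dependent variables will be examined for their relationship to dropout". The text then continues: "Those variables related to dropout status will be used to impute missing values for use in the analyses described (via SPSS Missing Items Analysis".
- Step 3 compares the results in completers with the imputed results.

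The text does not say whether imputation is single or multiple, whether it is done within arm, or which result prevails if the two analyses disagree. The Aim 3 text states the analysis principle as "All analyses will employ an intent-to-treat approach", and the effect tested is group condition, SBIRT-PN against TAU. The SAP repeats the Aim 3 analysis but says nothing about missing data. On the amount expected, Protocol section 25.0 (Retention) says "we anticipate a 10% dropout rate with a maximum dropout rate of 20% by time 3".

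**The concern.** An imputation model should contain at least the variables in the analysis it feeds. Aim 3 estimates a difference between arms, yet arm is neither a demographic nor an outcome variable, so step 2 never screens it. If arm is absent, missing values in both arms come from one pooled prediction. The imputed participants then carry no arm contrast of their own and pull the two group means together.

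Association with dropout is also a poor sole criterion for choosing predictors. Baseline use, likely to predict later use well, is passed over whenever it happens not to predict dropout.

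What is at stake is the size of the Aim 3 group effect: use days at follow-up and, if imputed in the same way, treatment engagement. A pilot estimate that is too small could also mislead the planning of a later trial.

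**Working it through.** The plan gives no power calculation, effect size, SD or imputation-bias figure, so there is nothing of its own to reproduce.

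**Inputs from the Protocol.** 90 participants (section 10.0) and equal allocation in blocks of 4 by site (section 6.0), so about 45 per arm. Dropout is 10% anticipated and 20% maximum (section 25.0), which is 9 to 18 people.

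**Assumptions.** Significance level 0.05 for screening dropout predictors; true effect 0.50 or 0.60 SD; correlation 0.5 between visits; dropouts share the completers' arm effect given the predictors.

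**1. Would arm get in?** Read literally, no, because it is not a step 2 candidate. On a broad reading, a significant step 1 test makes arm a variable associated with dropout. Exact enumeration over two binomials of 45 gives the chance that an uncorrected chi-square test flags arm:

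| Dropout in the two arms | Chance arm is flagged |
|---|---|
| 10% / 10% | 5.9% |
| 20% / 20% | 5.4% |
| 15% / 25% | 23% |
| 5% / 15% | 39% |
| 10% / 30% | 69% |

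With continuity correction the first two become 1.6% and 2.5%. Arm is normally left out unless dropout is very unbalanced.

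**2. Share of the effect kept without arm.** Let dT and dC be the dropout fractions and w = (1 - dT) / [(1 - dT) + (1 - dC)] the treated share of those observed. Both arms are filled in from the same pooled mean, so

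share kept = (1 - dT) + (dT - dC) × w, which is 1 - d when dT = dC = d.

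- d = 0.10: 0.90. d = 0.20: 0.80.
- dT = 0.10, dC = 0.30: 0.90 - 0.20 × (0.90/1.60) = 0.79.

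Simulation with a 0.50 SD effect (4,000 trials per scenario) agrees. Arm-blind imputation gave about 0.45 SD at 10% missing and 0.40 SD at 20%; observed data with baseline adjustment gave 0.50 SD in both.

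**3. If the 3-month outcome is observed and selected.** It carries the arm effect, so part of the contrast is recovered. With slope b for that predictor and the same effect at both visits, share kept = 1 - d(1 - b).

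- b = 0.3 to 0.7: 93-97% at d = 0.10 and 86-94% at d = 0.20.
- Simulation (0.60 SD effect, 1,500 trials, 10 imputations): 95% and 89%, Monte Carlo error about 1 point.
- With baseline as the only predictor, the same simulation kept 88% and 78%. The loss is therefore roughly halved.

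**4. Does multiple imputation alone cure it?** No. The 88% and 78% above are from multiple imputation. Adding arm restored 98% and 99%, matching the completers analysis in the same runs.

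**5. Type I error and power.**

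- Arm-blind single imputation (mean, deterministic regression or stochastic regression) held type I error near 5%, because under the null it treats the arms alike.
- At 20% missing and 0.50 SD, power was about 66% on observed data, about 57% with arm-blind stochastic regression and 66% with arm-blind deterministic regression. In the deterministic case the estimate shrinks by (1 - d) and its standard error by √(1 - d) from the full-data value, so the ratio is √(1 - d) times the full-data ratio, the same as for observed data.
- If arm is added but one deterministic imputation is treated as real data, the reported standard error is about (1 - d) times the correct one. The effective critical value becomes 1.96 × 0.9 = 1.764 or 1.96 × 0.8 = 1.568, that is, type I error of about 8% or 12%. Simulation (6,000 trials) gave 7.9% and 12.1%.

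**The case against.** Five points can be made for the plan.

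- **The rule does not say that nothing else enters the model.** This is true, and with the procedure named so briefly the final model is uncertain. It still states how predictors are chosen, names the candidate classes and omits the variable under test. That is a rule needing correction, not just absent detail. It supports the words not guaranteed and normally left out, but not a claim that arm is excluded in every case.
- **Outcome variables are candidates.** This stands: if the 3-month outcome enters, the loss roughly halves. It enters only if observed and found related to dropout.
- **Completers are also analysed.** This may expose a discrepancy but does not remove it, and the plan does not say which result prevails.
- **The error is small and conservative.** At 10% missing it is 0.05 SD against a standard error near 0.19 SD. That is fair for the test of one hypothesis, but a known and avoidable bias need not be accepted because it is smaller than the noise.
- **Aim 3 is secondary in a feasibility pilot.** This stands and limits the priority. However, H3 is still to be judged by F and p values.

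A reader might infer that following the rule as written both shrinks the effect and inflates false positives. The documents do not support that. The 8% and 12% arise only when arm is in the model and a single deterministic imputation is used; with arm left out, type I error stays near 5%. The two harms are alternatives. Nor can a general loss of power be claimed, because the plan does not say which type of imputation it will use.

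**Conclusion.** The concern holds in a limited form. As worded, the rule would normally leave arm out, and the imputed Aim 3 group effect would then keep about 90% of its true size at 10% dropout and about 80% at 20%. With the 3-month outcome observed and used as a predictor, it would keep about 95% and 89%. Any power loss depends on the imputation type, and type I error is unaffected while arm is out. A standard error that is too small is a separate hazard, to be avoided when arm is put in.

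These figures rest on dropouts sharing the completers' arm effect given the predictors and on the assumed effect size, correlations and screening level. The 20% is a maximum reached by the last visit, so an effect averaged over visits would shrink less if fewer are missing at 3 months. The primary outcomes, feasibility and acceptability, are not touched by this calculation.

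**What to change.** Amend the Missing Data paragraph of Protocol section 17.0 and carry it into the SAP, using one of two routes.

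- **Keep imputation.** Arm, site, baseline outcome and the other visit's outcome always enter the model, with dropout-related variables as extras. Use multiple imputation (for example 20 or more sets) combined by Rubin's rules.
- **Avoid imputation for the repeated substance-use outcome.** Use a likelihood-based (REML) mixed model on all observed visits, with arm, visit, arm-by-visit, baseline value and site. This is equally acceptable.

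In either case, state that this analysis is the main one for Aim 3 and keep the completers analysis as a sensitivity analysis. The step 1 comparison of dropout by arm can stay as description, but should not decide whether arm is in the model. The cost is wording and a little analysis time; no new data are needed.
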